1. BACKGROUND AND SIGNIFICANCE

Hypertensive diseases of pregnancy complicate around 10% of pregnancies. Preeclampsia is a pregnancy related hypertensive disorder. In the US during the past two decades the incidence of preeclampsia has increased by 25%. ¹The diagnosis of preeclampsia impacts the gestational age at delivery, with those with preeclampsia with severe features being delivered by 34 weeks gestational age, and those without being delivered by 37 weeks gestational age.² Preeclampsia is a major contributor to prematurity. Perinatal mortality is higher in infants of preeclamptic women regardless of gestational age at delivery. ³Causes are hypothesized as placental insufficiency and placental abruption, which in turn cause either intrauterine fetal demise, or early delivery. Preeclampsia may also cause serious maternal adverse effects including: eclampsia (seizures), posterior reversible encephalopathy syndrome, placental abruption leading to disseminated intravascular coagulopathy amongst other maternal adverse outcomes. It is also associated with long term maternal health consequences, including long-term cardiovascular disease risk. ²

Low dose aspirin was initially reported as having a beneficial effect at preeclampsia prevention in a case in 1978.⁴ Since then there have been large randomized controlled trials with conflicting results regarding effectiveness of aspirin for preeclampsia prevention, and the optimal dosing. (table 1)

Table 1: Placebo based randomized trials of ASA ≤100mg for preeclampsia prophylaxis

Study Location Year	N	Gestational Age At Enrollment	Comparison	Preeclampsia Outcome
Wallenburg et al Netherlands 1986 ⁵	46	28 weeks	60mg ASA	Preeclampsia occurred in 30% (placebo) vs 0% (ASA), p<0.01.
McParland et al UK 1990 ⁶	148	24 weeks	75mg ASA	Preeclampsia occurred in 25% (placebo) vs 13% (ASA), not significant.

CLASP⁷ Multicenter 1994	6927	12 -32 weeks	60 mg ASA	A nonsignificant reduction of 12% in rate of developing proteinuric pre-eclampsia.
ECPPA⁸ Brazil 1996	1009	12 – 32 weeks	60 mg ASA	No significant difference in rate of preE in both groups.

Rationale for a clinical trial

Evidence suggests that in preeclamptic patients there is an imbalance in the prostacyclin /thromboxane balance favoring thromboxane. Thromboxane is a vasoconstrictor while prostacyclin is a vasodilator.⁹ The pathophysiology of action of aspirin for preeclampsia prophylaxis is believed to be due to its preferential inhibition of COX-1 at low doses (60-150mg/day)¹⁰.

The American College of Obstetrics and Gynecology in July 2018, published a committee opinion supporting the USPSTF guideline criteria for the use of low dose aspirin for preeclampsia prophylaxis. The recommended dose is 81mg/day of aspirin, and it is to be used in women at high risk for preeclampsia. Women were considered to be at high risk if they had at least a 8% incidence of preeclampsia (table 2). The initiation of aspirin was to be done at 12-28 weeks gestation, optimally prior to 16 weeks gestational age.¹⁰

Table 2: ACOG recommendations for low dose aspirin (LDA) use for preeclampsia prophylaxis

Risk Level	Risk Factors	Recommendations
High	History of preeclampsia Type 1 or 2 Diabetes Chronic Hypertension Multifetal Gestation Renal Disease	LDA if \geq 1 Risk Factor

	Autoimmune Disease (SLE, APLS)	
Medium	BMI \geq 30	LDA if > 1 Risk Factor
	Nulliparity	
	Fam. Hx of preE (mother or sister)	
	Sociodemographic characteristics (AAF, low SES)	
	Age \geq 35	
	Personal Hx factors (hx of SGA , prior adverse pregnancy outcomes)	

As illustrated in table 3 there have been multiple randomized controlled trials that support the use of higher aspirin doses for preeclampsia prophylaxis. A recent systematic review and metaanalysis of randomized controlled trials, evaluating a total of 14,668 patients noted that the incidence of preeclampsia depended on the gestational age at initiation of aspirin and the dosing of aspirin used. With a clinically significant decrease in rate of preterm preeclampsia noted when the aspirin dose is ≥ 100 mg/day and when it is initiated at ≤ 16 weeks (table 4)¹¹.

Table 3: Randomized Trials with higher dose Aspirin for prevention of Preeclampsia

Study Location Year	Gestation al Age at enrollment	N	Comparison	Preeclamps ia Outcomes
Rolnik Multicenter Europe 2017¹²	11-14 weeks	1776	150mg ASA vs placebo	Preterm preeclampsia 4.3% in placebo group vs 1.6% in ASA

				group (p=0.0004)
Yu Multicenter International 2003¹³	22-24 weeks	844	150mg ASA vs placebo	19% in placebo group vs 19% in ASA group (p=0.6)
Sureau Multicenter France 1991¹⁴	15-18 weeks	229	150mg ASA vs 150mg ASA + dipyrimadole 225 mg/day vs placebo	No difference between groups.

Table 4: Metaanalysis with Relative Risk of preterm Preeclampsia detailed by onset of treatment and dose of aspirin

Dose	Trials Participants	Gestational Age	RR (95% CI)	P-value
< 100 mg	10 trials 11,855 pts	≤ 16 weeks	0.59 (0.29- 1.19)	0.14
		> 16 weeks	1.00 (0.80- 1.25)	0.99
≥ 100 mg	7 trials 2,813 pts	≤ 16 weeks	0.33 (0.19- 0.57)	0.001
		> 16 weeks	0.88 (0.54- 1.43)	0.60

Aspirin resistance is a phenomenon that refers to the inability of aspirin to reduce the production of thromboxane A2. It is detected by laboratory tests that either measure directly the thromboxane A2 levels, or indirectly the platelet function that depends on platelet thromboxane production.¹⁵ A recent study evaluated aspirin resistance in pregnant patients, and noted that aspirin resistance was decreased as the dosing of aspirin increased. With a incidence of 30% , 10% and 5% of aspirin resistance at doses

of 81, 121 and 162mg respectively.¹⁶ Moreover, data has emerged in other fields linking obesity, female gender, and poor glycemic control to aspirin resistance.¹⁷

At baseline, obesity is linked to a low grade inflammation state causing lipid peroxidation and in turn a persistent platelet activation, causing higher levels of thromboxane to be present in this population.¹⁸ Also, obesity is a established risk factor for preeclampsia.² In a population-based cohort study including 503,179 nulliparous patients, obese patients had a fourfold increase in incidence of preeclampsia in comparison to those with a normal BMI.¹⁹

A metaanalysis published in the lancet in 2018 highlighted the effects of the interaction between bodyweight and aspirin dose in reducing vascular events.²⁰ This study concluded that patients with higher body weights need a higher aspirin dosage for secondary cardiovascular prevention. While other fields are also realizing the impact of bodyweight on aspirin effectiveness, we argue that this concept should be extended to our high risk obese patient population. A population which also inherently has a higher incidence of preeclampsia, higher baseline thromboxane levels, and may also have higher aspirin resistance. We thus propose that a “one dose fit all” approach may not be appropriate in this patient population. To our knowledge, at this time there are no randomized controlled trials that have compared aspirin 81mg and 162 mg in the pregnant obese patient population.

Hypothesis

We hypothesize that the administration of a higher dose of aspirin prophylaxis to a high risk obese population will result in a clinically significant decrease in rate of developing preeclampsia with severe features in comparison to the standard 81mg/day dose.

2. RESEARCH DESIGN AND METHODS

Objective

To compare the incidence of preeclampsia with severe features in the 81mg/day aspirin group to the 162mg/day aspirin group. Maternal and neonatal outcomes will also be compared between the two groups.

Population

Obese pregnant women with a singleton gestation at less than 20 weeks and either a history of preeclampsia in a prior pregnancy or stage I hypertension or pre-gestational diabetes.

Obese is defined as a BMI greater than 30 at time of the first prenatal visit.

Intervention

Aspirin at a dose of 162mg/day (ie two 81mg/day pills daily) to be started as early as 12 weeks gestational age till time of delivery

Control

Women who receive the standard recommended 81 mg/day dosing of aspirin from as early as 12 weeks gestational age till time of delivery

Outcome (Primary)

Incidence of preeclampsia

Preeclampsia with severe features diagnosis will be abstracted from the medical charts. This will be used for the primary outcome. The diagnosis will then be adjudicated by three maternal fetal medicine specialists, to assess for compliance with ACOG established criteria.² The adjudicated diagnosis will be used for the measurement of the secondary outcome.

Other Secondary Outcomes

- Maternal Outcomes
 - o Incidence of preterm preeclampsia
 - o Gestational Hypertension
 - o Abruptio
 - o Eclampsia
 - o HELLP syndrome
 - o Postpartum Hemorrhage
 - o Other maternal bleeding (?)
 - o Need for blood transfusion
- Neonatal Outcomes
 - o Gestational age at delivery
 - o Delivery at < 37 weeks
 - o Apgar score at 5 min ≤ 5
 - o Small for gestational age
 - o NICU length of stay
 - o Intraventricular Hemorrhage Grade III-IV
 - o Bronchopulmonary Dysplasia
 - o Necrotizing Enterocolitis

Study Design

Randomized controlled open-label comparative effectiveness trial.

Inclusion Criteria

- A singleton gestation at less than 20 weeks at time of enrollment, with a BMI greater than or equal to 30 and one of the following:

1. History of preeclampsia in a prior pregnancy

-Diagnosis will be obtained by review of records, and if unavailable then patient history. Preeclampsia diagnosis may be made in antepartum or postpartum period.

OR

2. At least stage I hypertension during pregnancy

-Stage I hypertension is defined as a systolic blood pressure between 130-139 mm Hg or diastolic blood pressure between 80-89 mm Hg²¹

- This blood pressure criteria is met regardless of medication usage
- The patient must have a blood pressure reading $\geq 130-139/80-89$ mm Hg at least during 1 clinic visit during the current pregnancy; before or at time of enrollment

OR

3. Pre-gestational diabetes

- Type 1 and Type 2 diabetics are included
- Gestational diabetes mellitus diagnosed prior to 20 weeks gestational age will also be included

Exclusion Criteria

- ***Known allergy/prior adverse reaction/any medical condition where aspirin is contraindicated***
- ***Already on aspirin prior to pregnancy***
- ***Baseline renal Disease***
- ***Baseline Proteinuria identified at time of enrollment, defined as urine analysis with 3+ protein, or urine protein to creatinine ratio ≥ 0.3***
- ***Seizure disorder on medications***
- ***Known major fetal anomalies***
- ***Multifetal gestation***

Recruitment

Patients will be recruited from the following locations:

- Texas Medical center Ross Clinic in the UT Professional Building (Suite 350)
- Texas Medical center High Risk OB Clinic in the UT Professional Building (Suite 350)
- UT Obstetrics office at Bellaire
- Harris Health Obstetrics Clinic at LBJ Hospital

Randomization

Randomization will be achieved by computer-generated random sequences, using RedCap. Permuted block randomization will be performed. Women will be randomized to 81mg/day of aspirin or 162 mg/day of aspirin.

Interventions and Procedures

Women with singleton gestations that are less than twenty weeks gestational age and meet inclusion criteria will be approached by the research staff after the study is introduced by the patient's provider. Written informed consent will be obtained from participating women at the outpatient clinic. If the patient consents, then randomization

will be performed. The results of randomization will be shared with the obstetric provider and the patient prior to starting aspirin. If the patient had already been started on 81mg/day aspirin in a prior visit then she will be informed of whether she should continue with the same dose or if she would need a higher dose based on the randomization.

[figure not shown]
After randomization, patients will then be prescribed the medication. Which will be started between 12 and 20 weeks gestational age and continued till time of delivery. The primary provider will dictate all other aspects of care.

A medication adherence survey (Morisky medication adherence survey) will be performed to assess for compliance at 16-24 weeks of gestational age, and again at 32- 36 weeks gestational age. At the time of administration of medication adherence surveys, participants will be asked about medication side effects. ²²⁻²⁴

Blood samples (3-4 cc) and urine samples (3-4 cc) will be obtained at the time of enrollment (with the routine blood tests that are sent), to test for baseline aspirin, thromboxane and prostacyclin levels. At the time of delivery, blood samples (3-4 cc) and urine samples (3-4 cc) (with routine blood samples that are sent at time of labor admission), placental 1x1 cm specimens and cord blood will be obtained. These samples will be used for biochemical correlation with the clinical data.

The primary outcome (incidence of preeclampsia with severe features) will be determined based on clinician diagnosis, with the use of ACOG diagnostic criteria. Secondary outcomes will be determined by following the mother and the neonate clinically until the time of discharge. Patients will not be contacted after discharge from the hospital.

Figure 1. Flow Diagram

Sample Size and Feasibility

An intent-to-treat principle will be applied to all analysis. To calculate Bayesian statistical power we assumed a baseline incidence of preeclampsia in our population to be 20%. We investigated effects sizes of 50%, 40%, and 30% reduction (corresponding relative risk [RR] of 0.5, 0.6, and 0.7). We also varied the level of certainty (probability threshold for declaring benefit) from 70% to 85%. For all scenarios, we assumed a neutral prior centered at RR of 1.0 with 95% credible interval of 0.33-3.0 (excludes implausible large treatment effects). Tables 5 and 6 present the power for two total sample sizes. We will use the number of patients required to detect a 40% reduction in incidence of preeclampsia with 75% certainty and power $(1 - \beta) = 0.80$ is **220** (110 patients in each arm).

Table 5: Bayesian power for sample size N=290 using different levels of certainty

Assumed RR	Level of Certainty			
	70%	75%	80%	85%
0.50	0.97	0.95	0.93	0.89
0.60	0.91	0.88	0.83	0.76
0.70	0.80	0.75	0.68	0.59

Table 6: Bayesian power for sample size N=220 using different levels of certainty

Assumed RR	Level of Certainty			
	70%	75%	80%	85%
0.50	0.93	0.9	0.86	0.81
0.60	0.84	0.80	0.74	0.67
0.70	0.71	0.66	0.59	0.5

In the week of November 5-9 2018, 10 patients that attended the UT Women's clinic and UT Bellaire Clinic, met inclusion criteria. Assuming a 50% enrollment rate, the study would take 12.5 months.

Statistical Tests

Selected baseline characteristics and outcome measures will be collected for each group. Descriptive statistics will be used to summarize all variables. An intent-to-treat analysis will be conducted. The rate of the primary outcome, preeclampsia, will be compared between the intervention and control group using a log binomial (or Poisson in case of nonconvergence) model to estimate relative risk and 95% confidence interval (CI). Each secondary outcome will be similarly analyzed using the best fitting generalized linear model with intervention group as the covariate. For all outcomes, we will report relative risks or differences and 95% CIs.

We will also conduct a Bayesian analysis of the primary outcome to calculate probability of treatment benefit or harm. We will use a neutral prior distribution for the intervention effect that excludes implausible large treatment effects: Normal(0, SD=0.57) in the log RR scale (prior 95% interval for the RR of 0.33-3)²⁵. We will report posterior median and 95% credible interval and probability of treatment benefit.

Subgroup Analysis. To investigate treatment effect modifier for the primary outcome, we will use a Bayesian hierarchical model with terms of interaction between treatment group (162 mg, 81 mg) and the prespecified potential moderator of BMI (30-40; >40). The conservative Bayesian approach of Dixon and Simon²⁶ allows us to specify a priori how likely (or unlikely) it is for subgroup differences to be present and to shrink the subgroup estimates to the overall mean treatment effect. A neutral prior will be used for the interaction term. Point estimates of treatment effect and 95% credible intervals will be reported along with probability of treatment benefit/harm.

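### The primary endpoint is preeclampsia with severe features in some places and unqualified preeclampsia in others, and the plan does not say which event the 20% control rate, and so the 0.80 power, refers to

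*Combined protocol and SAP*

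**What the plan says.** All places are in the combined protocol and SAP.

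Four statements name severe features:
- Section 1, Hypothesis: a "clinically significant decrease in rate of developing preeclampsia with severe features in comparison to the standard 81mg/day dose".
- Section 2, Objective: "To compare the incidence of preeclampsia with severe features in the 81mg/day aspirin group to the 162mg/day aspirin group".
- Section 2, Outcome (Primary), text below the outcome line: "Preeclampsia with severe features diagnosis will be abstracted from the medical charts. This will be used for the primary outcome".
- Section 2, Interventions and Procedures: "The primary outcome (incidence of preeclampsia with severe features) will be determined based on clinician diagnosis, with the use of ACOG diagnostic criteria".

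Four statements use the bare term:
- Section 2, Outcome (Primary), the outcome line itself: "incidence of preeclampsia".
- Section 2, Sample Size and Feasibility, control rate: "we assumed a baseline incidence of preeclampsia in our population to be 20" percent.
- Section 2, Sample Size and Feasibility, effect: the sample size is the number needed to "detect a 40% reduction in incidence of preeclampsia with 75% certainty".
- Section 2, Statistical Tests: "The rate of the primary outcome, preeclampsia, will be compared between the intervention and control group".

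The opening paragraph of Section 1 treats these as different conditions. It gives one delivery time for preeclampsia with severe features and a later one for preeclampsia without them.

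**The concern.** Preeclampsia with severe features is a subset of preeclampsia, so the two names count different events. Two things follow.

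First, Statistical Tests is the instruction to the analyst. The Bayesian analysis and the BMI subgroup analysis in that section also take the primary outcome as their input, so all of them inherit whichever meaning is given to it. The trial is open-label and the outcome is a clinician's diagnosis taken from charts. Two available readings would leave room to choose between them once results are known.

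Second, the planned power is tied to the 20%. If that figure is the rate of all preeclampsia, the 0.80 describes an endpoint other than the one in the hypothesis. If it is the severe-features rate, the power is right and only the label is wrong. The plan gives no source for the 20% and no severe-features rate anywhere. The outcome rates in Tables 1 and 3 are for preeclampsia or preterm preeclampsia.

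**Working it through.** **Inputs.** From Sample Size and Feasibility: 110 women per arm, control rate 20%, relative risk (RR) 0.6, benefit declared at 75% certainty, stated power 0.80. From Statistical Tests: prior for log RR Normal(0, SD 0.57), which matches the 0.33 to 3.0 interval used for the power calculation.

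**Method.** Let x_c ~ Bin(110, p) be events on 81 mg and x_t ~ Bin(110, RR × p) events on 162 mg. For each pair of counts:
- estimate L = log(x_t / x_c), with variance v = 1/x_t − 1/110 + 1/x_c − 1/110 (0.5 added if either count is zero);
- posterior precision k = 1/v + 1/0.57², posterior mean m = (L/v)/k;
- declare benefit if P(RR < 1) = Φ(−m√k) > 0.75.

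Power is the summed probability of the pairs for which benefit is declared. The normal likelihood is an assumption, because the plan does not state its algorithm. The next step tests it.

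**Reproducing the plan.** At p = 0.20 and RR 0.6 the result is 0.796, which rounds to the stated 0.80. All 24 cells of Tables 5 and 6 are reproduced within 0.009. A closed form agrees: with s² = 0.80/(110 × 0.20) + 0.88/(110 × 0.12) = 0.1030, s = 0.321, power = Φ((0.511 − 0.674 × 0.321 × √(1 + 0.1030/0.3249))/0.321) = Φ(0.817) = 0.793. The tables are therefore right for an endpoint with a 20% control rate, whichever endpoint that is.

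**Sensitivity, N=220, 75% certainty.** Every control rate below 20% is an assumption, since the plan gives no severe-features rate.

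| Control rate | Expected events at RR 0.6 (81 mg / 162 mg) | Power, RR 0.5 | Power, RR 0.6 | Power, RR 0.7 |
|---|---|---|---|---|
| 20% | 22.0 / 13.2 | 0.904 | 0.796 | 0.652 |
| 18% | 19.8 / 11.9 | 0.883 | 0.768 | 0.622 |
| 15% | 16.5 / 9.9 | 0.841 | 0.724 | 0.585 |
| 10% | 11.0 / 6.6 | 0.695 | 0.587 | 0.478 |

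Expected events are 110 × p and 110 × 0.6 × p. The answer also depends on the RR, and nothing in the plan says that the RR for severe features equals that for any preeclampsia. At RR 0.5, power stays above 0.80 down to a control rate of 14% (0.821) and is 0.797 at 13%.

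**The case against.** The strongest reply is that the endpoint is already settled. Two of the severe-features statements are operative: one says which diagnosis is abstracted and used for the primary outcome, the other defines the primary outcome in brackets. The outcome line is only a heading to the text that specifies it, and Statistical Tests refers back to the primary outcome, so its bare word may be shorthand. Any preeclampsia is given no ascertainment rule and is not listed as a secondary outcome.

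Most of this stands. The weight of the text does make severe features the primary endpoint. A reader might infer that the analyst is bound to test the wrong endpoint; the documents do not support that, because reaching it means passing over both definitions. They support only that the analysis sentence could be read that way.

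A reader might also infer that the trial is underpowered. That is not supported either. The 0.80 is correct at 20%, and every lower figure needs a control rate that the plan does not give. The missing citation carries little weight by itself, since the 20% is openly presented as an assumption.

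What the reply does not answer is which event the 20% counts. Read literally it is any preeclampsia; read as shorthand it is severe features. The text allows both, and only the sponsor can say which was meant.

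**Conclusion.** The inconsistency is real and must be corrected. The primary endpoint carries two names of different breadth, and the bare term occurs in at least four places, including the analysis model. This rests on the wording alone.

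The effect on power is conditional. If 20% is the severe-features rate, 0.80 stands. If 20% is the any-preeclampsia rate and the severe-features rate is lower, then with RR held at 0.6 and certainty at 75%, power at N=220 is below the stated 0.80, by an amount that the documents do not allow one to fix. At an assumed 18% the difference is about 0.03, and at an assumed 15% about 0.07 to 0.08. Confidence is high in the naming conflict and the arithmetic, and the severity does not depend on any power loss.

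**What to change.** 1. Write preeclampsia with severe features in the line under Outcome (Primary) and in the primary-outcome sentence of Statistical Tests, to match the hypothesis, objective, ascertainment rule and procedures.
2. Before the sample-size text is changed, have the sponsor state which event the 20% counts and on what basis. Relabelling first could turn an any-preeclampsia rate into a severe-features rate.
3. If it is the severe-features rate, correct both mentions in Sample Size and Feasibility (the 20% rate and the 40% reduction); 0.80 stands. If it is the any-preeclampsia rate, leave it labelled as such, state the expected severe-features rate on 81 mg, rerun Tables 5 and 6 at that rate, and restate the power at N=220.

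The cost is two wording changes and one statement from the sponsor, followed by either two more wording changes or an added rate and a rerun of two tables. The downside is a possibly lower stated power; restating it discloses that power and does not repair it. No added enrolment is proposed.

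### Does the 12.5-month duration, which does not follow from 5 enrolments a week and 220 women, call for a change to the plan?

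*Combined protocol and SAP*

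**What the plan says.** Under Sample Size and Feasibility (section 2, Research Design and Methods), the plan chooses its sample size from Bayesian power tables: the number required "is 220 (110 patients in each arm"). A larger size was also tabulated, under the title "Bayesian power for sample size N=290 using different levels of certainty", but was not chosen.

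The accrual estimate follows the tables. Its input is a single week's count: "In the week of November 5-9 2018, 10 patients that attended the UT Women's clinic and UT Bellaire Clinic, met inclusion criteria". Its conclusion is: "Assuming a 50% enrollment rate, the study would take 12.5 months". The plan gives no attrition allowance, start-up period or number of weeks per month.

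Three other places in section 2 bear on how long the trial lasts:

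- Inclusion Criteria: "A singleton gestation at less than 20 weeks at time of enrollment".
- Interventions and Procedures, on aspirin: "Which will be started between 12 and 20 weeks gestational age and continued till time of delivery".
- The same part, on the end of follow-up: "Secondary outcomes will be determined by following the mother and the neonate clinically until the time of discharge".

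**The concern.** A feasibility figure should follow from the inputs printed beside it, and this one does not. It matches neither 220 nor 290. If an attrition allowance had been applied silently, the true enrolment target would differ from 220 and the reader could not tell.

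The sentence also speaks of how long the study takes, although the last woman enrolled still has to be followed to delivery and discharge. The rate is fragile too: it counts women who attended clinics in one week, and some may have been returning patients who would appear again in later weeks.

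This is the only feasibility statement in the document. If it were badly optimistic, recruitment could fall short of 220, and the stated power of 0.80 would go with it.

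**Working it through.** **Inputs from the plan (section 2).** Eligible women: 10 a week. Enrolment rate: 50%. Planned N: 220. Tabulated alternative: 290. Enrolment before 20 weeks; aspirin starts at 12 to 20 weeks. From section 1, Background: delivery by 34 weeks with severe features and by 37 weeks without.

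**Assumptions.** Delivery at 40 weeks for women without preeclampsia, which the plan does not give. Weeks per month: 4, or 365.25/7/12 = 4.348 for calendar months.

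**Attempt to reproduce 12.5 months.** Enrolments a week = 10 × 0.5 = 5. Accrual in weeks = N / 5.

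| N | Weeks | Four-week months | Calendar months |
|---|---|---|---|
| 220 | 220/5 = 44 | 44/4 = 11.0 | 44/4.348 = 10.1 |
| 290 | 290/5 = 58 | 58/4 = 14.5 | 58/4.348 = 13.3 |

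Neither row gives 12.5.

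**Working back.** N = 12.5 × weeks per month × 5.

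- Four-week months: 12.5 × 4 × 5 = 250.
- Calendar months: 12.5 × 4.348 × 5 ≈ 272.

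A 12% attrition allowance would turn 220 into 250 (220/0.88 = 250), and about 19% would give 272. The plan states neither.

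**Reading 1: the figure is accrual time.** It exceeds what 220 women need by 12.5 − 11.0 = 1.5 months (four-week) or 12.5 − 10.1 = 2.4 months (calendar). The error is on the cautious side. Enrolling 220 in 12.5 months requires only 220/50 = 4.4 a week (four-week months) or 220/54.35 ≈ 4.0 a week (calendar months), against the 5 assumed.

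**Reading 2: the figure is time to completion.** After 44 weeks of accrual there remain 50 − 44 = 6 weeks (four-week months) or 54.35 − 44 ≈ 10.4 weeks (calendar months). A last woman enrolled just under 20 weeks would then be at about 26 to 30 weeks, usually still undelivered. Time to the last delivery is:

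| Last enrolment | Delivery | Added weeks | Total weeks | Calendar months | Four-week months |
|---|---|---|---|---|---|
| just under 20 | 34 | 14 | 58 | 13.3 | 14.5 |
| just under 20 | 37 | 17 | 61 | 14.0 | 15.25 |
| just under 20 | 40 (assumed) | 20 | 64 | 14.7 | 16.0 |
| 12 | 40 (assumed) | 28 | 72 | 16.6 | 18.0 |

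Time to discharge is extra. The last row is not a strict maximum, because the inclusion criteria set no lower limit on gestation at enrolment.

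**Reliability of the weekly rate.** If each eligible woman attended twice within the window (an assumption), new enrolments would be 2.5 a week, and 220 would take 220/2.5 = 88 weeks, about 20 calendar months. In the other direction, Recruitment lists four locations, including the clinic at LBJ Hospital, while the count names two clinics and not LBJ. The documents do not show which effect is larger.

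**Does anything depend on 12.5 months?** The sample size does not. A simulation with a Normal(0, 0.57) prior on the log relative risk, a 20% control rate, relative risk 0.6, 110 women per arm and a 75% threshold gives power 0.795, against 0.80 in Table 6. Thus 220 stands on its own inputs, and calendar time is not among them. The Statistical Tests section does not use the duration, and no section ends recruitment at a date.

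**The case for a change.** The best case for a change is that neither reading rescues the figure: it is too long for accrual of 220 and too short for completion. Staffing, funding and the expected date of the last primary outcome might lean on it, the correction costs one sentence, and a hidden 12% allowance would mean an enrolment target of 250.

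The arithmetic in that case stands. The consequences do not:

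- The plan states 220 outright, with the split per arm. A back-calculated 250 depends on four-week months and is no evidence of another target.
- A slow clinic would put recruitment at risk whatever this sentence said. The sentence neither causes the risk nor sets a deadline that would cut the sample short.
- The 20-month scenario rests on an assumed two visits per woman and leaves out the site missing from the count.
- A corrected sentence would still rest on one week's count and an assumed delivery time. It would be tidier but hardly more reliable as a forecast, and actual accrual would soon supersede it.

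**Conclusion.** The inconsistency is confirmed. At 5 enrolments a week, 220 women take 44 weeks (10.1 calendar or 11.0 four-week months), not 12.5 months. As an accrual time the stated figure is 1.5 to 2.4 months too long. As a time to completion it is too short: by about 0.8 to 4.1 calendar months (13.3 − 12.5 to 16.6 − 12.5), before discharge, if the last woman enrols between 12 and just under 20 weeks and delivers between 34 and 40 weeks. The 40-week point is an assumption.

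No change to the plan follows. The figure is a rough planning estimate. Correcting it would leave the sample size, power, 75% threshold, outcome definitions and analysis exactly as they are, and would change no result the trial reports. Those running the trial can replace it with observed accrual and follow each woman to discharge as the plan already requires. The 44-week calculation is certain given the plan's inputs. The true weekly rate is not, and could be higher or lower.
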